Long-term Pelvic Floor and Sexual Health After Obstetric Anal Sphincter Injury in Finland

[name]¹, [name]^{1,2}, [name]², [name]²

¹Center for Child, Adolescent and Maternal Health Research, Faculty of Medicine and Health Technology, Tampere University, Tampere, Finland ²Department of Obstetrics and Gynecology, Tampere University Hospital, The Wellbeing Services County of Pirkanmaa, Tampere, Finland

Study protocol

Version 1, 26.1.2026

Background

In Finland, anal sphincter rupture occurs in approximately 1.6% of vaginal deliveries.¹ Perineal tears are typically repaired immediately in the delivery room, and sphincter injuries are most often repaired shortly after delivery in an operating room. It is important to attempt to prevent sphincter injuries, as damage to the anal sphincter is a significant cause of fecal incontinence in women, which negatively affects quality of life in many ways. In previous data from Tampere University Hospital (Tays), 64% of women were asymptomatic six months after sphincter repair, whereas 36% continued to experience symptoms.²

Previous studies suggest that prior sphincter injury affects the number of children women have.³ Many women report that symptoms following sphincter injury significantly reduce their quality of life.⁴ Common symptoms include inability to control stool or gas,⁵ but sexual dysfunction and overall impact on quality of life have also been reported.

A Dutch study assessed sexual function and quality of life 2–11 years after injury using questionnaires. Sexual dysfunction was reported by 19 out of 32 respondents.⁶ In this study, more severe tears were associated with poorer quality-of-life scores. Similarly, a French study reported that 17 out of 160 women experienced frequent dyspareunia and 24 out of 160 suffered from chronic pelvic pain 1–12 years after injury.⁷

International studies suggest that fecal incontinence is more common following more severe tears.⁸ On the other hand, most women appear to remain asymptomatic in long-term follow-up.⁹ Episiotomy has been considered protective against sphincter injury but has been associated with an increased risk of long-term fecal incontinence. Evidence regarding its effects on sexuality is inconsistent, although it has been linked to dyspareunia.¹⁰¹¹¹²

International findings are difficult to generalize to Nordic countries, particularly Finland, due to differences in childbirth practices. In Nordic countries, midwives play a significantly larger role, operative deliveries are less frequent, and high-quality care is universally available. Finnish midwives traditionally support the perineum carefully during birth (“Finnish maneuver”), and adoption of this technique has reduced tear rates in Norway.¹³

There is limited Finnish research on the long-term consequences of sphincter injuries. This study forms the second and third parts of a three-part doctoral thesis. The first publication examined mode of delivery and recurrence risk in subsequent deliveries following sphincter injury. The majority (78%) of women planned vaginal delivery, and recurrence was rare (1.9%). The article was published in July 2025 in *BMC Pregnancy and Childbirth*.¹⁴

Objectives

The aims of this study are to:

- determine the prevalence of long-term pelvic floor symptoms and sexual dysfunction after sphincter injury
- identify factors that predispose to long-term symptoms
- assess the impact of sphincter injury on desired family size and identify factors associated with having fewer children than planned
- evaluate satisfaction with mode of delivery choice in a subsequent delivery and associated factors

Materials and Methods

The study population consists of individuals who gave birth at Tays between 2009 and 2021 and whose delivery was complicated by sphincter injury (n = 580). Data on all pregnancies and births treated at Tays for these individuals will be collected from patient records.

Participants will receive by mail an information sheet, a consent form, and two questionnaires:

- PISQ-12 (assessing sexual function)
- PFDI-20 (assessing pelvic floor dysfunction)

These questionnaires have also been validated in Finnish.¹⁵ Additional questions will address family size, and women who have delivered after the injury will be asked about their choice of delivery mode.

Participants may return paper forms or complete the consent and questionnaires electronically. A reminder will be sent once if no response is received within two months.

Personal identifiers will be replaced with study IDs, and data will be processed in pseudonymized form. Data will be stored and analyzed in a secure environment. Questionnaire responses will be compared with clinical background data to identify risk factors for long-term symptoms, reduced family size, and satisfaction with delivery mode choice. Statistical analyses will be performed using SPSS.

Paper questionnaires will be stored securely in locked facilities. After the active phase, electronic data will be archived, and all data will be destroyed upon completion of the study.

Timeline and Implementation

Ethics approval will be sought in early 2026. After approval, questionnaires will be distributed. Data collection is planned for 2026, with articles written during 2027–2028.

The study will be conducted at the Faculty of Medicine at Tampere University as part of a doctoral project supervised by [name] (MD, PhD) and Docent [name]. Articles will be submitted to high-quality international journals.

Strengths and Limitations

This study will provide important information on long-term consequences of sphincter injury among Finnish women. Detailed clinical data combined with questionnaire responses will enable identification of risk factors. The results may improve targeted rehabilitation and prevention strategies.

References

1. Perinataaltilasto – synnyttäjät, synnytykset ja vastasyntyneet. THL. October 6, 2025. Accessed November 5, 2025. <https://thl.fi/tilastot-ja-data/tilastot-aiheittain/seksuaali-ja-lisaantymisterveys/synnyttajat-synnytykset-ja-vastasyntyneet/perinataaltilasto-synnyttajat-synnytykset-ja-vastasyntyneet>
2. Kuismanen K. Synnytys ja sulkijalihasrepeämä. *Duodecim*. 2019;135:818-823.

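### The long-term outcome spans about 4 to 18 years after injury, with no stated time frame and no described way to identify women who are pregnant or recently delivered when they answer

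*Protocol*

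**What the plan says.** The first objective is to "determine the prevalence of long-term pelvic floor symptoms and sexual dysfunction after sphincter injury"; the second is to "identify factors that predispose to long-term symptoms". Neither gives a time point, a time window or a definition of long-term.

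Materials and Methods sets the cohort: "The study population consists of individuals who gave birth at Tays between 2009 and 2021" with a sphincter injury at that delivery, 580 in all. They receive PISQ-12, PFDI-20 and additional questions. The additional questions cover family size and, for women who delivered again, their choice of delivery mode. There is one mailing and one reminder. Record data are limited to pregnancies and births treated at the study hospital (Tays).

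Timeline and Implementation fixes the survey date: "Ethics approval will be sought in early 2026. After approval, questionnaires will be distributed", and "Data collection is planned for 2026". For risk factors, the plan is to compare responses with clinical background data; no covariates are named. Strengths and Limitations does not mention the spread of follow-up.

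**The concern.** Two features of the design combine.

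- **No time frame.** Thirteen years of injuries are surveyed in one calendar year, so each woman's follow-up is set almost entirely by her year of injury. A pooled prevalence averages over this range, and a reader cannot tell what length of follow-up it describes.
- **No way to set temporary symptoms apart.** Women who have given birth again stay in the population, and no minimum interval since the latest birth is set. A woman who is pregnant or has recently delivered may report symptoms that belong to that pregnancy or birth. If she is under care elsewhere, the records will not show it, and the described questionnaire does not ask.

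The second feature is the more urgent. Strata and model terms can be chosen later from data already held. A question left out of a single mailing cannot be recovered by analysis. Both the prevalence and the risk-factor results depend on this outcome.

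**Working it through.** The protocol gives no sample-size or precision figure to reproduce, so the check starts from its dates.

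**1. Follow-up range.** Inputs: deliveries from 1 January 2009 to 31 December 2021 (Materials and Methods); survey during 2026, after ethics approval (Timeline and Implementation). Years since injury = survey date minus delivery date.

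| Survey date | Shortest (years) | Longest (years) |
|---|---|---|
| 1 March 2026 | 4.2 | 17.2 |
| 1 July 2026 | 4.5 | 17.5 |
| 31 December 2026 | 5.0 | 18.0 |

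The range is about 4 to 18 years. For any one survey date the longest follow-up is about four times the shortest (17.2/4.2 = 4.1; 18.0/5.0 = 3.6).

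**2. Calendar period and time since injury.** In whole years, time since injury = 2026 − year of injury. The correlation between the two is −1.0. No stratification or adjustment within this survey can separate them.

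**3. What a pooled figure can hide.** The only symptom prevalence from this hospital is 36% at six months (Background), used here purely as an illustration. With equal injuries per year and an assumed logistic trend, a pooled 36% fits each of these:

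| Assumed odds ratio per 10 years | At 5 years | At 17 years |
|---|---|---|
| 1.0 (no trend) | 36.0% | 36.0% |
| 1.5 | 30.5% | 41.7% |
| 2.0 | 26.9% | 45.8% |
| 3.0 | 22.1% | 51.5% |

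The documents do not say which row applies.

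**4. Women pregnant or recently delivered.** Let f be their share of responders and d the difference in prevalence between them and the other women. The pooled prevalence then shifts by f × d. The documents give neither f nor d. A bound is possible: if the other women have 36%, d is at most 100 − 36 = 64 points. To reach the sampling half-width of 5.5 points at 290 responders (step 5), f must be at least 5.5/64 = 8.6%, or about 25 women (0.086 × 290), and that is with every one of them symptomatic. The shift is therefore probably modest, but without the question it cannot be shown.

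**5. Precision.** Half-width = 1.96 × √(0.36 × 0.64/n) = 0.941/√n. Response is assumed at 50% (290 of 580), with 30% and 70% as a range. By calendar-year difference, the 4–7 band holds 3 injury years (2019–2021), and the 8–12 and 13–17 bands hold 5 each. With equal injuries per year, 290 responders split as 290 × 3/13 = 67 and 290 × 5/13 = 112 twice.

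| Responders | Pooled half-width | 4–7 years | 8–12 and 13–17 years, each |
|---|---|---|---|
| 174 (30%) | 7.1 points | 14.8 (n = 40) | 11.5 (n = 67) |
| 290 (50%) | 5.5 points | 11.5 (n = 67) | 8.9 (n = 112) |
| 406 (70%) | 4.7 points | 9.7 (n = 94) | 7.5 (n = 156) |

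At 290 responders, the difference between the outer bands has half-width 1.96 × √(0.2304/67 + 0.2304/112) = 14.5 points. The bands describe the data; they are weak as a test for trend.

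**6. Age terms.** Age at survey = age at delivery + years since injury. All three cannot enter one linear model.

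**The case against.** Much of this can be left to a statistical analysis plan, which may exist but is not shown. The protocol does not say that only one pooled figure will be reported or that time since injury will be ignored. Delivery dates are in the records, so prevalence by follow-up and adjustment remain open. That stands, and the reporting and model terms are recommendations rather than faults.

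Prevalence in 2026 among women injured in 2009–2021 is a defined cross-sectional quantity, and the Dutch and French studies cited in the Background span 2–11 and 1–12 years. That also stands: a wide range is usual and does not invalidate the figure. It still needs to be stated and described.

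Recent births are partly covered, because births at Tays are in the records, women who delivered again receive extra questions, and the exact wording of those questions is not shown. This narrows the gap without closing it. Births and pregnancies cared for elsewhere are outside the records, and the described questions concern family size and choice of delivery mode, not current pregnancy or the date of the latest birth.

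A reader might infer that risk factors will be confounded by changes in practice over 2009–2021. The documents do not support that. They describe no change at Tays in episiotomy, instrument use, grading or repair, and they give no trend of symptoms with time. Confounding of this kind is possible but not shown.

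**Conclusion.** The concern holds in a limited form. The protocol fixes a follow-up range of about 4 to 18 years without stating a time frame or a minimum interval since the latest birth. As described, it cannot identify every woman who is pregnant or recently delivered when she answers. This follows from the dates and the listed data sources and rests on no assumed effect.

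The size is not known. A reader might assume a trend of 1 point per year and take the resulting gap of 12 points between the 2009 and 2021 injuries (12 × 1) as an error in the prevalence. It is not one: the slope has no source in the documents and may be zero, and the gap is a spread within the cohort. It should not be set against the 5.5-point sampling half-width as if both measured error in the pooled figure. The precision figures rest on an assumed 50% response, equal injuries per year and 36% prevalence.

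The pregnancy and recent-birth question should be settled before mailing. The rest can be done afterwards from data already held.

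**What to change.** Before mailing:

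- Add one question: current pregnancy, or a birth in the last 12 months, at any hospital.
- State in the objectives that long-term means about 4 to 18 years since injury, as observed in 2026.

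In the analysis:

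- Repeat the main prevalence without women who answer yes to the new question, as a sensitivity analysis.
- Report the distribution of years since injury, and prevalence by years since injury (for example 4–7, 8–12 and 13–17) beside the pooled figure.
- Include years since injury in the risk-factor models, with either age at delivery or age at survey, not both.
- State as a limitation that one survey year cannot separate calendar period from time since injury.

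The cost is one questionnaire item, one model term and less precise estimates within bands. No further record data are needed.
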